5.5.6 Exploratory Efficacy Analysis

The number and percentage of subjects meeting the below the specified criteria are summarized by visit:

- Subjects responding to treatment during Phase A by visit as specified in Section 3.2.
- Subjects meeting stabilization criteria of MADRS and CGI-S at any point during Phase B Section 3.3.
- Subjects achieving remission at any time point during Phase B.

Subjects achieving remission in Phase B is defined as a MADRS total score ≤ 10.

5.6 Safety Analysis

Standard safety variables to be analyzed include AEs, clinical laboratory tests, vital signs, ECGs, body weight, waist circumference, and BMI. In addition, data from the following safety scales will be evaluated: Simpson-Angus Scale (SAS) Total Score, Abnormal Involuntary Movement Scale (AIMS) Total Score, Barnes Akathisia Rating Scale (BARS), and C-SSRS.

In general, safety analysis will be summarized for Phase B safety sample and Phase C safety sample respectively. Listing of safety variables for Phase A safety sample will be

provided. Baseline for Phase A safety sample will be used as the baseline for safety analysis in Phase B as well. Baseline for Phase C safety sample is defined as the last visit with available data in Phase B prior to the first dose in Phase C.

5.6.1 Adverse Events

All adverse events (AE) will be coded by MedDRA System Organ Class (SOC) and Preferred Term (PT). A treatment-emergent AE (TEAE) is defined as an AE which starts after start of trial medication), or an AE continues from baseline of the specific phase and becomes serious, worsening, trial drug-related or results in death, discontinuation, interruption or reduction of trial medication during this phase. The incidences of the following treatment-emergent adverse events (TEAEs) will be summarized by treatment groups:

- TEAEs by severity
- Potentially drug related TEAEs
- TEAEs with an outcome of death
- Serious TEAEs
- Discontinuations due to TEAEs

Listing and incidences of AEs above will be tabulated by treatment for Phase B safety sample and Phase C safety sample, respectively. Deaths, SAEs, and AEs leading to discontinuation from trial will be listed by phase for the enrolled sample.

5.6.2 Laboratory Test Results

Clinical laboratory tests include the routine clinical laboratory measurements, prolactin concentrations, coagulation parameters (PT, aPTT, and INR), HbA1c, cortisol, ACTH, and TSH as well as laboratory tests identified using prospectively defined criteria.

Summary statistics for the clinical laboratory measurements at baseline and post-baseline visits, and summary statistics of changes from baseline to each visit will be presented by treatment group. Incidence of treatment-emergent potentially clinically significant abnormal lab results will also be summarized by treatment groups. Listings of potentially clinically significant abnormalities will also be provided. Criteria of potentially clinically significant lab test abnormalities are provided in Appendix 1.

According to FDA Guidance, laboratory measurements that signal the potential for drug-induced liver injury (DILI) will be reported. An incidence table and a listing will be provided for subjects who meet one or combinations of following criteria:

- 1) ALT or AST $\geq 3 \times$ upper limit of normal (ULN) or baseline value

- 2) increase in bilirubin $\geq 2 \times$ ULN or baseline value

If laboratory tests assessments are repeated for the same visit, the last repeated values are used for summary tables. This is accomplished by sorting patient data by visit date and visit time (if applicable) within the same visit identification. If the lab data are recorded as ranges (i.e., including < or > limit of quantification), these data are not included in the calculations for changes from baseline but included in the calculations for incidences.

Listings and summary tables of clinical laboratory measurements will be presented for Phase B safety sample and Phase C safety sample respectively. Potentially clinically significant laboratory abnormalities for Phase A safety sample will be provided by listings.

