^cVital signs include body weight, body temperature, SBP, DBP, and heart rate. Blood pressure and heart rate will be measured in the following order: supine, sitting, and standing after the subject has been in each position for at least 3 minutes. Vital signs scheduled for the same visit as blood samples are to be completed before blood is drawn.

^dStandard 12-lead ECGs will be performed after the subject has been supine and at rest for ≥ 5 minutes prior to the ECG. ECG results will be evaluated at the investigational site to monitor safety. A central ECG service will be utilized to review all ECGs in order to standardize interpretations for the safety analysis. The ECG is to be completed before any blood sample is collected.

^eBlood samples for clinical laboratory tests should be drawn after the subject has been fasting for at least 8 hours, if possible. If fasting blood samples are not feasible, nonfasting blood samples may be collected. Vital sign and ECG assessments should be completed before any blood samples are collected.

^fA urine drug screen and a blood alcohol test are required at the designated times, but either or both can be conducted at any time during the trial at the discretion of the investigator.

Protocol 331-201-00079

^gAll positive urine pregnancy test results must be confirmed by a serum test. Subjects with a positive serum pregnancy test result during the trial must discontinue treatment and be withdrawn from the trial. Pregnancy tests can be performed at any point during the trial if pregnancy is suspected.

[REDACTED]

Protocol 331-201-00079

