3.7.1.3 Stabilization Phase, Week 9 through Week 20/Randomization (Phase B)

The following assessments will occur during the Stabilization Phase:

- A qualified and certified rater will administer the MADRS *at Weeks 9 through 20*.
- The investigator (or qualified designee) will administer the CGI-S *at Weeks 9 through 20*.
- The subject will complete the SDS *at Weeks 9, 14, and 20*.
- A complete physical examination (including waist circumference) will be performed *at Week 20 only*.
- Vital sign measurements (body weight, body temperature, blood pressure, and heart rate) will be recorded *at Weeks 9 through 20*. Blood pressure and heart rate are to be measured in the following order: supine, sitting, and standing after the subject has been in each position at least 3 minutes. Vital signs are to be completed before any blood is drawn.
- A standard 12-lead ECG will be performed after the subject has been supine and at rest for at least 5 minutes *at Week 16*. The ECG is to be completed before any blood sample is collected.
- A fasting blood draw must be collected for clinical laboratory tests (hematology and serum chemistry) and urine will be collected for urinalysis *at Week 20*. The laboratory tests will include prolactin. Vital sign and ECG assessments should be completed before any blood samples are collected.
- Blood samples will be drawn for PK analysis *at Weeks 16 and 20*.
- A urine drug screen will be performed *at Week 16*.
- A urinary pregnancy test (WOCBP only) will be performed *at Weeks 12, 16, and 20*. Any positive result must be confirmed by a serum pregnancy test. WOCBP with a positive serum pregnancy test result must discontinue the IMP and be withdrawn from the trial.
- A qualified and certified rater will administer the SAS, AIMS, and BARS *at Weeks 12 and 20*.
- The investigator (or qualified designee) who is adequately trained will complete the “Since Last Visit” C-SSRS form *at Weeks 9 through 20*.
- Adverse events and concomitant medications will be recorded *at Weeks 9 through 20*.
- IMP will be dispensed to the subject *at Weeks 9 through 20*.
- Drug accountability will be performed *at Weeks 9 through 20*.
- Subjects will be randomized at the *Week 20/Randomization visit*.
- [REDACTED]
- Blood sample will be drawn for pharmacogenomic analysis at the *Week 20/Randomization visit*. If a subject early terminates at Week 20, no sample will be collected.

Protocol 331-201-00079

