3.7.1.4 Double-blind Randomized Withdrawal Phase (Week 21 through Week 46/End of Phase C/Relapse) (Phase C)

The following assessments will occur during the Double-blind Randomized Withdrawal Phase:

- A qualified and certified rater will administer the MADRS *at Weeks 21 through 46*.
- The investigator (or qualified designee) will administer the CGI-S *at Weeks 21 through 46*.
- The subject will complete the SDS *at Weeks 21 through 46*.
- For subjects who discontinue early, attempts should be made to complete ALL evaluations, particularly efficacy assessments (ie, MADRS, CGI-S, and SDS), for the *Week 46/ET* visit prior to the administration of any new antidepressant medications. However, if the subject receives a new antidepressant prior to ET procedures, no efficacy assessments should be done.
- A complete physical examination (including waist circumference) will be performed *at Week 46 only*.
- Vital sign measurements (body weight, body temperature, blood pressure, and heart rate) will be recorded *at Weeks 21 through 46*. Blood pressure and heart rate are to be measured in the following order: supine, sitting, and standing after the subject has been in each position at least 3 minutes. Vital signs are to be completed before any blood is drawn.
- A standard 12-lead ECG will be performed after the subject has been supine and at rest for at least 5 minutes *at Weeks 29 and 46*. The ECG is to be completed before any blood sample is collected.
- A fasting blood draw should be collected for clinical laboratory tests (hematology and serum chemistry) and urine will be collected for urinalysis *at Week 46*. If fasting blood samples are not feasible, nonfasting blood samples may be collected. The laboratory tests will also include prolactin *at Week 46*. Vital sign and ECG assessments should be completed before any blood samples are collected.
- Blood alcohol will be tested *at Week 46*.
- Blood samples will be drawn for PK analysis *at Weeks 37 and 46*.
- A urine drug screen will be performed *at Weeks 33 and 46*.
- A urinary pregnancy test (WOCBP only) will be performed *at Weeks 33 and 46*. Any positive result must be confirmed by a serum pregnancy test. WOCBP with a positive serum pregnancy test result must discontinue the IMP and be withdrawn from the trial.

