3.7.3.2 Clinical Laboratory Assessments

A central laboratory designated by the sponsor will be used for all laboratory testing required during the trial. The central laboratory should be used for all laboratory testing whenever possible (including unscheduled and follow-up, if needed). In cases where an immediate result is required for a particular laboratory test, the sample should be divided and sent to both a local laboratory and the designated central laboratory. Subjects should be fasting for a minimum of 8 hours prior to the blood draws, if possible. If fasting blood samples are not feasible at screening, nonfasting blood samples may be obtained initially

Protocol 331-201-00079

for determining eligibility for the trial. The results of these tests at screening must be reviewed by the investigator prior to initiation of the administration of the IMP.

Additional urine and blood samples may be collected for further evaluation of safety as warranted by the investigator's judgment. Reports from the central laboratory should be filed with the source documents for each subject. The central laboratory will provide laboratory results to the sponsor electronically. A list of clinical laboratory assessments is provided in [Table 3.7.3.2-1](#).

Table 3.7.3.2-1 Clinical Laboratory Assessments

Hematology: WBC count with differential RBC count Hematocrit Hemoglobin Platelet count	Serum Chemistry: ALP ALT Albumin AST Bicarbonate Bilirubin, total BUN CPK Calcium Chloride Cholesterol (total, low density lipoprotein, and high density lipoprotein) Creatinine GGT Glucose Inorganic phosphorus Insulin LDH Magnesium Potassium Protein, total Sodium TSH
Urinalysis: pH Specific Gravity Protein Ketones Glucose Blood Microscopic analysis (performed only if any part of the urinalysis is not negative)	Cholesterol (total, low density lipoprotein, and high density lipoprotein) Creatinine GGT Glucose Inorganic phosphorus Insulin LDH Magnesium Potassium Protein, total Sodium TSH
Urine Drug Screens: Amphetamines Barbiturates Benzodiazepines Cannabinoids Cocaine Marijuana Methadone Opiates Phencyclidine Propoxyphene	T ₄ (if needed) Uric acid Triglycerides
Other: Blood Alcohol	Additional Tests: Urine or serum pregnancy for WOCBP PT aPTT INR HbA1c Prolactin
	Additional Tests (screening only): HIV HbsAg anti-HCV

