Appendix 1 Criteria for Identifying Laboratory Values of Potential Clinical Relevance

Laboratory Tests	Criteria
Chemistry	
AST (SGOT)	≥ 3 x upper limit of normal (ULN)
ALT (SGPT)	≥ 3 x ULN
Alkaline phosphatase	≥ 3 x ULN
LDH	≥ 3 x ULN
BUN	≥ 30 mg/dL
Creatinine	≥ 2.0 mg/dL
Uric Acid	
Men	≥ 10.5 mg/dL
Women	≥ 8.5 mg/dL
Bilirubin (total)	≥ 2.0 mg/dL
CPK	≥ 3 x ULN
Prolactin	> ULN
Hematology	
Hematocrit	
Men	≤ 37 % and decrease of ≥ 3 percentage points from baseline
Women	≤ 32 % and decrease of ≥ 3 percentage points from baseline
Hemoglobin	
Men	≤ 11.5 g/dL
Women	≤ 9.5 g/dL
White blood count	≤ 2,800/ mm ³ or ≥ 16,000/ mm ³
Eosinophils	≥ 10%
Neutrophils	≤ 15%
Absolute neutrophil count	≤ 1,000/ mm ³
Platelet count	≤ 75,000/ mm ³ or ≥ 700,000/ mm ³
Urinalysis	
Protein	Increase of ≥ 2 units
Glucose	Increase of ≥ 2 units
Casts	Increase of ≥ 2 units
Additional Criteria	
Chloride	≤ 90 mEq/L or ≥ 118 mEq/L
Potassium	≤ 2.5 mEq/L or ≥ 6.5 mEq/L
Sodium	≤ 126 mEq/L or ≥ 156 mEq/L
Calcium	≤ 8.2 mg/dL or ≥ 12 mg/dL
Glucose	
Fasting	≥ 100 mg/dL
Non-Fasting	≥ 200 mg/dL
Total Cholesterol, Fasting	≥ 240 mg/dL
LDL Cholesterol, Fasting	≥ 160 mg/dL
HDL Cholesterol, Fasting	
Men	< 40 mg/dL
Women	< 50 mg/dL
Triglycerides, Fasting	≥ 150 mg/dL

Protocol 331-201-00079

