5.1.3 Handling of Missing Data

For missing data resulting from early withdrawal from the trial in Phase C, subjects who withdraw early will be censored in the primary efficacy analysis at the time when they withdraw from the trial. For other efficacy variables, two types of analyses will be performed for analyses by visit in Phases B and C: LOCF and OC. The LOCF and OC data sets are defined in Section 5.1.1. The OC data set will be used for analyses at each trial visit and the LOCF data set will be used for analyses at the last visit.

The definitions of weeks for Phase A, B and C are described in the following Table 5.1.3-1 and Table 5.1.3-2. Trial Days are derived for each phase from the formula: Trial Day = Date of assessment - Date of 1st brexpiprazole dosing + 1 in Phase A or B, or Date of randomization in Phase C. Based on the number of trial days, subjects are mapped to the corresponding week in each phase in the summary tables. Only last observation within the same week in each phase is used for the summary tables. The LOCF/OC datasets for Phase A consist of data values obtained from visits at Phase A baseline, and week 1 through week 8 in Phase A. The LOCF/OC datasets for Phase B consist of data values obtained from week 1 through week 12 in Phase B and Phase A baseline as the baseline. The LOCF/OC datasets for Phase C consist of data values obtained from visits (after randomization) from week 2 through week 26 in Phase C (study Week 21 – Week 46).

Note: NA = Not Applicable.

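### Phase C change in glucose, insulin and lipids runs from a compulsory fasting Week 20 sample to an end sample that may be nonfasting, and the SAP does not separate the two

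*SAP*

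**What the plan says.** **Baseline.** Protocol 3.7.1.3 states for Week 20: "A fasting blood draw must be collected for clinical laboratory tests (hematology and serum chemistry". Footnote f of Table 3.7-2 makes the same demand, with a minimum fast of 8 hours. SAP 5.6 sets the reference value: "Baseline for Phase C safety sample is defined as the last visit with available data in Phase B prior to the first dose". Week 20 is the only chemistry draw scheduled in Phase B, so in practice it is the Phase C baseline.

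**End of Phase C.** Table 3.7-3 schedules one chemistry draw, at the Week 46/ET/relapse visit. Protocol 3.7.1.4 weakens the verb: "A fasting blood draw should be collected for clinical laboratory tests (hematology and serum chemistry". Footnote e of Table 3.7-3 adds: "If fasting blood samples are not feasible, nonfasting blood samples may be collected". The Phase C schedule in the COVID-19 addendum repeats this permission.

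**Analytes.** Protocol Table 3.7.3.2-1 includes glucose, insulin, triglycerides and the cholesterol fractions.

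**Analysis.** SAP 5.6.2 plans that "summary statistics of changes from baseline to each visit will be presented by treatment group". Neither it nor Protocol 7.6.2 mentions fasting status for these summaries.

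**Abnormality criteria.** Protocol Appendix 1 does use fasting status. It has separate fasting (≥ 100 mg/dL) and non-fasting (≥ 200 mg/dL) glucose limits, and its lipid rows are fasting only, for example "Total Cholesterol, Fasting".

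**The concern.** A change score is interpretable only if both measurements are taken under comparable conditions. Here the first is fasting by rule and the second is fasting only if feasible. For a subject whose end sample is nonfasting, the reported change in a food-sensitive analyte is the true change plus the effect of a meal, and the planned table gives no means of telling them apart.

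Safety and tolerability is the trial's secondary objective, and Phase C is its only placebo-controlled part. The supplied Table 3.7-3 has no HbA1c row and Protocol 3.7.1.4 does not mention HbA1c, so no scheduled glycaemic measure independent of recent food intake stands beside glucose in that phase.

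Two things are at stake. Increases within each arm may be overstated. If the share of nonfasting samples differs by arm, the arm difference may also be shifted.

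**Working it through.** The documents give no nonfasting rate, meal effect or expected metabolic change, so there is no planned figure to reproduce. The calculation shows what the permission could do under stated assumptions.

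**Inputs from the documents**
- Assumed 6-month relapse, p: 0.16 on brexpiprazole and 0.30 on placebo (Protocol 7.1, SAP 4).
- Assumed loss to follow-up: 20% (Protocol 7.1, SAP 4).

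**Inputs assumed here**
- Nonfasting share of Week 46 samples, w: 10–20%.
- Nonfasting share of relapse-visit samples, r: 30–80%.
- Mean fed-minus-fasted shift, S: 15–30 mg/dL for glucose and 40–80 mg/dL for triglycerides.

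**Step 1: nonfasting share per arm in a last-visit summary**, f = p·r + (1 − p)·w.
- Brexpiprazole: from 0.16×0.30 + 0.84×0.10 = 13.2% to 0.16×0.80 + 0.84×0.20 = 29.6%.
- Placebo: from 0.30×0.30 + 0.70×0.10 = 16.0% to 0.30×0.80 + 0.70×0.20 = 38.0%.

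**Step 2: overstatement within an arm**, f·S.
- Glucose: brexpiprazole 0.132×15 = 2.0 to 0.296×30 = 8.9 mg/dL; placebo 0.160×15 = 2.4 to 0.380×30 = 11.4 mg/dL.
- Triglycerides: brexpiprazole 0.132×40 = 5.3 to 0.296×80 = 23.7 mg/dL; placebo 0.160×40 = 6.4 to 0.380×80 = 30.4 mg/dL.

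**Step 3: shift in the arm difference.** The excess nonfasting share on placebo is (0.30 − 0.16)·(r − w) = 0.14·(r − w).
- Smallest r − w is 30% − 20% = 10 points: 0.14×0.10 = 0.014.
- Largest is 80% − 10% = 70 points: 0.14×0.70 = 0.098.
- Glucose: 0.014×15 = 0.2 to 0.098×30 = 2.9 mg/dL.
- Triglycerides: 0.014×40 = 0.6 to 0.098×80 = 7.8 mg/dL.

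Brexpiprazole minus placebo is lowered by this amount. If brexpiprazole truly raises the analyte, that is a bias towards no difference.

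**Step 4: add the 20% loss, equal in both arms.**
- Lost subjects give no sample: early-visit samples are 0.16/(0.16 + 0.84×0.80) = 19.2% on brexpiprazole and 0.30/(0.30 + 0.70×0.80) = 34.9% on placebo.
- Lost subjects all give an ET sample with the same nonfasting rate as a relapse visit: 0.16 + 0.20×0.84 = 32.8% and 0.30 + 0.20×0.70 = 44.0%.
- The factor 0.14 becomes 0.157 or 0.112. The upper ends become 3.3 or 2.4 mg/dL for glucose and 8.8 or 6.3 mg/dL for triglycerides, so the order of magnitude is unchanged.

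**Step 5: null cases.**
- If r = w, the arm difference has no bias and both arms are overstated equally.
- If no end sample is nonfasting, f = 0 and both bias terms are zero.
- Within fasting-to-fasting pairs f = 0 by construction.

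**Step 6: which table is affected.** SAP 5.1.3 states: "Based on the number of trial days, subjects are mapped to the corresponding week in each phase in the summary tables". A relapse or ET sample therefore falls in the week when it was drawn. The Week 46 row holds mainly completers, and the relapse imbalance in Step 3 does not enter it. Step 3 applies to a last-visit summary. SAP 5.1.2 defines the last visit for safety analyses, but SAP 5.6.2 does not explicitly request such a table. Step 2 concerns both kinds of table, with f specific to the row.

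**The case against.** The strongest reply is that fasting remains the default at the end visit, nonfasting is an exception, and no document says how often it will be used. That stands: a meal effect is possible under the plan, not established, and it may be negligible.

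A reader might go further and infer that metabolic harm will be hidden. The documents do not support this. For analytes that rise after food, the direct effect is an overstated increase in each arm. Masking of the arm difference needs more nonfasting samples on placebo. The assumed 30% against 16% relapse makes that possible, but nothing in the plan says that relapse visits are more often nonfasting. An excess of other early terminations on brexpiprazole would push the other way. By-visit tables are also largely protected from this mechanism by the week mapping.

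A reader might also infer that the abnormality incidence tables miscount nonfasting subjects. SAP 5.6.2 takes its criteria from SAP Appendix 1, which is not in the supplied text, and it states no laboratory denominator. No claim is made on those tables. Protocol Appendix 1 does separate fasting from non-fasting values, which implies that fasting status is meant to be known.

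Other evidence exists as well. Phase B change runs between two compulsory fasting samples for subjects reaching Week 20, though without a placebo control. Weight and waist circumference in Phase C do not depend on the laboratory fasting rule.

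Finally, restricting the comparison to fasting pairs selects on something observed after randomization and could remove more placebo relapsers. This objection is sound and shapes the fix: the fasting table should be added, not substituted.

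**Conclusion.** The concern holds in a limited form. The plan pairs a compulsory fasting baseline with an end sample that may be nonfasting, and it summarises all samples together. Change in glucose, insulin and triglycerides can therefore include a meal effect and be overstated in both arms. No size is derived for insulin or the cholesterol fractions.

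On the assumed inputs, a last-visit arm difference would be biased by about 0.2–2.9 mg/dL for glucose and 0.6–7.8 mg/dL for triglycerides. These ranges rest on assumed nonfasting rates and meal effects and on the planned relapse rates; none is an estimate from the trial. The lower bound is zero once equal nonfasting shares are allowed.

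The consequence is confined to descriptive safety tables for food-sensitive analytes. The primary analysis is not affected. The change is still worth making, because without it a reader of the Phase C tables cannot separate a metabolic change from a recent meal.

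**What to change.** In SAP 5.6.2:

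- Keep the all-subject change-from-baseline table.
- Add Phase C change from baseline in glucose, insulin, triglycerides and cholesterol fractions by fasting status, with fasting-to-fasting pairs as the main display for these analytes.
- Report the number and share of fasting Week 46/ET samples by arm.
- For any criterion defined for fasting samples only, use as denominator the subjects with at least one fasting on-treatment sample.

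This changes only the analysis; no sampling or clinical rule is altered. It requires fasting status to be available in the laboratory data, which Protocol Appendix 1 implies but which should be confirmed.

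The cost is some SAP text and one more set of laboratory tables. The fasting subset is smaller and is selected after randomization, so it should be read beside the all-subject table.

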5.4 Potential Serious Hepatotoxicity

For a subject who experiences an elevation in AST or ALT that is ≥ 3 times the ULN, a total bilirubin level should also be evaluated. If the total bilirubin is ≥ 2 times the ULN, complete an IRE form with all values listed and also report as an AE on the eSource.

Protocol 331-201-00079

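### SAP 5.6.2 can count in-range ALT, AST or bilirubin values as potential liver-injury cases through an unrestricted multiple of baseline, and its last-repeat rule can drop a value that crossed the threshold

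*SAP*

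**What the plan says.** SAP 5.6.2 (Laboratory Test Results) plans a DILI display: "An incidence table and a listing will be provided for subjects who meet one or combinations of following criteria". The two criteria are "ALT or AST $\geq 3 \times$ upper limit of normal (ULN) or baseline value" and "increase in bilirubin $\geq 2 \times$ ULN or baseline value". The first takes its multiple of the "upper limit of normal (ULN) or baseline value", and the second offers the same alternative. The same section says that when tests are repeated at one visit, "the last repeated values are used for summary tables". It separately plans incidence by treatment group of potentially clinically significant laboratory abnormalities under its Appendix 1.

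The protocol's liver criteria are these:

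- Section 5.4 (Potential Serious Hepatotoxicity) starts from "an elevation in AST or ALT that is ≥ 3 times the ULN", has bilirubin evaluated, and continues: "If the total bilirubin is ≥ 2 times the ULN, complete an IRE form".
- Appendix 1 uses 3 × ULN for AST and ALT, and an absolute 2.0 mg/dL for total bilirubin.

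Neither has a baseline alternative.

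**The concern.** The baseline alternative in SAP 5.6.2 stands on its own. Nothing confines it to subjects who start above normal, and nothing requires the later value to be abnormal. A subject with a low-normal start who moves to a mid-normal value can be tabulated as a potential liver-injury case. The entry criteria cap ALT and AST from above only (more than 2 × ULN is exclusionary), so low baselines are eligible.

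Two further points affect the same table. The bilirubin criterion speaks of an *increase*, which can be read as a level reached or as a change from baseline, and two programmers could reasonably produce different counts. The last-repeat rule covers summary tables without exempting incidence tables, so a first value over threshold could be replaced by a lower repeat. A display meant to surface a rare, serious signal could therefore include unremarkable values and miss a notable one.

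**Working it through.** The plan states no figure for this display, so there is none to reproduce. The check is threshold arithmetic, an illustration of chance, and a comparison of the repeat rules.

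**Step 1. Effective thresholds.** Let L be ULN and b the subject's baseline. Read literally, *or* means that the lower threshold applies.

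| Test | SAP 5.6.2 trigger | Protocol 5.4 threshold | In-range value can trigger when |
|---|---|---|---|
| ALT or AST | min(3L, 3b) | 3L | 3b ≤ L, so b ≤ L/3 |
| Bilirubin, level reading | min(2L, 2b) | 2L | 2b ≤ L, so b ≤ L/2 |
| Bilirubin, change reading | min(b + 2L, 3b) | 2L | 3b ≤ L, so b ≤ L/3 |

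In every row the baseline limb is the lower one only if b < L. It therefore acts only on subjects with a normal baseline; for an elevated baseline the ULN limb already governs.

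The documents give no ULN values, so these are assumptions:

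- ALT ULN of 35, 40 or 55 U/L: an in-range trigger is possible at a baseline up to 11.7, 13.3 or 18.3 U/L. With ULN 40, a move from 12 to 36 U/L is 3 × baseline but 36/40 = 0.9 × ULN. The protocol threshold would be 120 U/L.
- Bilirubin ULN of 1.0, 1.2 or 1.3 mg/dL: the baseline limit is 0.50, 0.60 or 0.65 mg/dL on the level reading, and 0.33, 0.40 or 0.43 on the change reading. With ULN 1.2, a move from 0.4 to 0.8 mg/dL is 2 × baseline but 0.8/1.2 = 0.67 × ULN. Protocol 5.4 would need 2.4 mg/dL. On the change reading this subject would not be flagged until 3 × 0.4 = 1.2 mg/dL.

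**Step 2. Chance flags for bilirubin.** Assume log-normal within-subject variation, no drug effect and one later sample. One sample fits the schedule: Protocol Tables 3.7-2 and 3.7-3 place routine laboratory tests once in Phase B (Week 20) and once in Phase C (Week 46/ET). The CVs are assumptions.

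SD of a log value: s = √ln(1 + CV²). SD of the log ratio of two values: d = √2 × s. Chance of a ratio of at least r: 1 − Φ(ln r / d), with r = 2 for the level reading and r = 3 for the change reading. The counts use the 450 subjects projected for randomization.

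| CV | d | z, r = 2 | Level reading | Of 450 | z, r = 3 | Change reading | Of 450 |
|---|---|---|---|---|---|---|---|
| 20% | 0.280 | 2.48 | 0.7% | 3 | 3.92 | 0.004% | 0.02 |
| 25% | 0.348 | 1.99 | 2.3% | 10 | 3.16 | 0.08% | 0.4 |
| 35% | 0.481 | 1.44 | 7.5% | 34 | 2.29 | 1.1% | 5 |

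**Step 3. How many of these are in range.** Step 2 has no baseline distribution, so it cannot say. A simulation adds one, again by assumption: log-normal true levels with median 0.4 × ULN for bilirubin (log SD 0.40) and 0.5 × ULN for ALT (log SD 0.45).

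- Bilirubin, level reading, CV 20% to 35%: 0.6% to 6.2% of subjects are flagged with an in-range value, about 1 to 14 per arm of 225. In the same runs 0.02% to 0.11% reach 2 × ULN.
- ALT, CV 20% to 40%: 0.002% to 1.1% are flagged with an in-range value.

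The exposure is mainly through bilirubin.

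**Step 4. The repeat rule beside its neighbours.**

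- SAP 5.6.2 (laboratory): the last same-visit repeat feeds summary tables, with no exception for incidence. The same paragraph does separate incidence from change for results recorded as limits, but not for repeats.
- SAP 5.6.3 (vital signs): the last repeat is used for mean change from baseline.
- SAP 5.6.4 (ECG): incidence counts patients with at least one abnormality in the period.

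Protocol 3.7.3.2 permits repeating a questionable result. If a first ALT over 3 × ULN is lower on a repeat filed under the same visit, SAP 5.6.2 as worded removes it from the incidence count.

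**The case against.** The strongest reply is that little is lost. The baseline limb only adds subjects; it removes nobody at or above 3 × ULN. A listing accompanies the table, and a separate incidence table by arm under Appendix 1 criteria is already planned. That stands, with two limits: the SAP's own Appendix 1 is not in the supplied text, and the planned table sits in the same section and is exposed to the same repeat rule.

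Second, the bilirubin wording may mean a change, which cuts the chance rate to about 1.1% or less. That also stands. It leaves the criterion ambiguous.

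Third, Protocol 5.4 is an immediate-reporting rule that needs both elevations, whereas the SAP rule is a tabulation met by either. The two would differ in count even with identical thresholds, so this is not a direct contradiction. What remains is that no protocol liver criterion uses a baseline multiple.

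Fourth, the repeat rule covers only repeats under the same visit and names summary tables, not listings. A later unscheduled test need not displace the scheduled value, so the loss is possible rather than certain.

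A reader might go further and infer that the table will consist mostly of normal variation, or that a true difference between arms will be diluted. The documents do not support this. They give no within-subject variability, no ULN and no expected number of true cases; Phase B has a single arm, and in Phase C chance flags are expected equally in both arms. Nor can it be said that the SAP departs from the FDA guidance it invokes, since that guidance is not available here.

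**Conclusion.** The point holds as a defect of definition in a descriptive safety table. As written, SAP 5.6.2 can flag a subject whose liver values are all normal, and the baseline limb operates only in subjects whose baseline is below ULN. The sponsor may have meant it only for elevated baselines, but the SAP does not say so.

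The size depends on the reading of *increase* and on an assumed bilirubin CV of 20% to 35%, one post-baseline sample and no drug effect. The range runs from about 3 to 34 chance flags among 450 subjects on the level reading down to about 0.02 to 5 on the change reading. For ALT the effect is small. The repeat rule can also lose a same-visit first value over threshold; how often cannot be estimated from the documents. The primary analysis is not affected.

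**What to change.** In SAP 5.6.2:

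1. Define the DILI criteria as ALT or AST at least 3 × ULN, and a total bilirubin level (not change) of at least 2 × ULN. Report the combination of both as its own row.
2. If a multiple of baseline is wanted, show it as a separate labelled row limited to subjects whose baseline exceeds ULN.
3. Count incidence from any on-treatment value, including repeats. Keep the last-repeat rule for mean-change tables only, in line with SAP 5.6.3 and 5.6.4.

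The cost is SAP wording, table shells and programming. No new data are needed.
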